8.2 EXCLUSION CRITERIA

Subjects who meet **ANY** of the following exclusion criteria must be excluded from the study:

1. History of meningococcal disease.

2. Current or recent systemic infection within 2 weeks prior to Screening or infection requiring intravenous (IV) antibiotics within 4 weeks prior to Screening.
3. Pregnant, planning to become pregnant, or nursing female subjects.
4. Recent surgery requiring general anesthesia within 2 weeks prior to Screening or expected to have surgery requiring general anesthesia during the 8-week Treatment Period.
5. Treatment with a complement inhibitor or an experimental drug within 30 days or 5 half-lives of the drug (whichever is longer) prior to Baseline.
6. Statin use within 30 days prior to Baseline or anticipated to occur during study.
7. Rituximab use within 90 days prior to Baseline or anticipated to occur during study.
NOTE: In subjects who received rituximab more than 90 days but less than 6 months prior to Baseline, prophylactic antibiotics (e.g., ciprofloxacin, erythromycin, penicillin V) should be given upon initiation of study drug until 6 months after the last rituximab dose
8. Recent initiation of intravenous immunoglobulin (IVIG) (i.e., first cycle administered less than 90 days prior to Baseline).
9. Plasma exchange within 4 weeks prior to Baseline or expected to occur during the 8-week Treatment Period.
10. Active malignancy (except curatively resected squamous or basal cell carcinoma of the skin) requiring surgery, chemotherapy, or radiation within the prior 12 months (subjects with a history of malignancy who have undergone curative resection or otherwise not requiring treatment for at least 12 months prior to Screening with no detectable recurrence are allowed).
11. History of any significant medical, psychiatric disorder, or laboratory abnormality that in the opinion of the investigator would make the subject unsuitable for participation in the study.
12. Participation in another concurrent clinical trial involving an experimental therapeutic intervention (participation in observational studies and/or registry studies is permitted).
13. Unable or unwilling to comply with the requirements of the study.
14. Subjects who have a known hypersensitivity to zilucoplan or any of its excipients.

8.3 SELECTION CRITERIA FOR THE EXTENSION PORTION

1. Completion of the Main Portion of the study.
2. Continues to meet inclusion criteria 2, 11, and 12 from the Main Portion of the study.
 2. *Able to provide informed consent, including signing and dating the ICF.*
 11. *Female subjects of childbearing potential must have a negative serum pregnancy test at Screening and a negative urine pregnancy test within 24 hours prior to the first dose of study drug.*
 12. *Sexually active female subjects of childbearing potential (i.e., women who are not postmenopausal or who have not had a hysterectomy, bilateral oophorectomy, or bilateral tubal ligation) and all male subjects (who have not been surgically sterilized by vasectomy) must agree to use effective contraception during the study. Postmenopausal women are, for the purposes of this protocol, defined as women who have gone 12 consecutive months without menstruation.*

3. Did not start any disallowed medication per the exclusion criteria from the Main Portion of the study or alter the dose of any other concomitant medication, unless medically indicated.
4. Is able and willing to comply with the requirements of the study.
5. Does not have any new medical condition (since entry into the Main Portion) or any other reason that, in the opinion of the investigator or Sponsor, would disqualify the subject from participation in the Extension Portion of the study.

8.4 REMOVAL OF SUBJECTS IN THE STUDY

8.4.1 WITHDRAWAL OF CONSENT

A subject may withdraw consent to participate in this study at any time without penalty or loss of benefits to which the subject is otherwise entitled to. When a subject wishes to withdraw consent, it is important to distinguish between withdrawing his/her consent for a particular study procedure or visit versus withdrawing his/her consent from the study entirely (i.e., premature discontinuation).

When a subject withdraws consent from the study (or study procedure), the reason(s) for withdrawal will be recorded by the investigator or designee on the relevant page of the electronic case report form (eCRF).

8.4.2 PREMATURE DISCONTINUATION

Every reasonable effort should be made to encourage retention of subjects in the study, maximize compliance with study drug, and facilitate attendance at all scheduled study visits/assessments.

All subjects have the right to refuse further participation in the study at any time and for any reason. A subject's participation must, therefore, be terminated immediately upon his/her request.

The investigator will make every attempt to ascertain the reason(s) for discontinuation and to document this in detail in the source documentation and the appropriate sections of the eCRF. A subject must be withdrawn from the study for any of the following reasons:

- Withdrawal by subject
- Protocol Violation/Noncompliance (defined as refusal or inability to adhere to the study procedures)
- Pregnancy while receiving study drug
- At the request of the Sponsor, regulatory agencies, or IRB/IEC
- Physician decision
- Loss to follow-up
- Death

Subjects may be withdrawn from study treatment due to unacceptable or intolerable AEs.

All subjects who permanently discontinue study treatment in the Main Portion of the study (i.e., prior to Day 57 visit) for any reason will not be eligible to participate in the Extension Portion of the study.

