12.2.5.1 PRIMARY EFFICACY ANALYSES

The primary efficacy endpoint, percent reduction from baseline in creatine kinase at Week 8, will be compared between the two treatment groups using a 2-sided stratified Wilcoxon rank sum test (Van Elteren test). Magnitude of treatment effect will be shown by the WMWodds and the Hodges-Lehman estimator followed by the corresponding 95% Confidence Intervals (CIs).

Definition of primary estimand:

- Treatment: zilucoplan administered by daily SC injection (0.3 mg/kg) vs matching placebo.
- Target Population: is defined through the inclusion/exclusion criteria at Sections 8.1 and 8.2 of the study protocol reflecting the targeted IMNM population.
- Endpoint: percentage change from Baseline to Week 8 in CK levels while on non-prohibited medication.
- Intercurrent event: regardless of any treatment discontinuation for any reason; censoring after prohibited medication
- Population level summary: difference in ranks of the percentage change from baseline between treatments followed by the WMWodds and Hodges–Lehmann estimator followed by the corresponding 95% CIs.

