12.3 SAMPLE SIZE DETERMINATION

A sample size of 12 subjects per group yields approximately 95% power to detect a difference in the percent reduction from baseline in creatine kinase between the active and placebo groups using a Wilcoxon rank sum test at the two-sided 0.05 type 1 error rate. The power calculations assume that the percent reduction in creatine kinase in the active dose group is approximately normally distributed with a mean of 80% and a standard deviation of 8%; that 4 of the placebo patients will have a percent reduction similar to the active dose group; and the remaining 8 placebo patients will have a percent reduction that is normally distributed with a mean of 10% and a standard deviation of 8% (Mammen and Tiniakou 2015).

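### Protocol 8.4.2, 7.2.2.2 and Table 1 stop scheduled follow-up for subjects who leave early, so the Week 8 outcome the estimands require is either missing or taken early

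*Protocol*

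**What the plan says.** **Withdrawal rule.** Protocol 8.4.2: "A subject must be withdrawn from the study for any of the following reasons". The list includes withdrawal by the subject, loss to follow-up and death. It also includes pregnancy on drug, physician decision, requests from the sponsor, regulators or the IRB/IEC, and "Protocol Violation/Noncompliance (defined as refusal or inability to adhere to the study procedures". Adverse events come in a separate sentence as an optional reason to leave study treatment. Section 8.4.1 treats premature discontinuation, the title of 8.4.2, as leaving the study altogether.

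**Visits after stopping drug.** Protocol 7.2.2.2 (which refers to 8.4.2) and Table 1 footnote 1-a ask for one End of Main Visit and a safety visit 40 days after the last dose. The safety visit has no CK or efficacy assessment. No other Main Portion visit is provided for.

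**Estimand.** Protocol 12.2.5.1 handles intercurrent events "regardless of any treatment discontinuation for any reason; censoring after prohibited medication". Protocol 12.2.5.2 and SAP 5.3 and 5.4.1 take the same approach.

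**Analysis.** SAP 5.1 makes the main analysis observed-case, and SAP 5.1.1.8.1 rules out multiple imputation for it. SAP 5.1.1.2.3 assigns an early End of Main assessment to the next visit at which that assessment is scheduled. LOCF is supplementary (SAP 5.3.4, 5.4.5). The trimmed-means analysis of CK runs only if at least 15% lack evaluable Week 8 CK (SAP 5.3.3). The secondary endpoints have no sensitivity analysis (SAP 5.4.4).

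**The concern.** A treatment-policy strategy for discontinuation depends on outcomes collected after drug is stopped. Read together, these sections do not arrange for that. Section 8.4.2 ends participation for some reasons that would not prevent a Week 8 blood draw, and 7.2.2.2 replaces the remaining schedule with one early visit for anyone who stops drug, including for an adverse event.

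Physician decision and inability to adhere can depend on response or tolerability, so the resulting gaps may be informative. Losing non-improving placebo subjects would make placebo look better than it was; losing non-improving zilucoplan subjects would do the same for zilucoplan. With 12 per arm, a few such subjects matter for both bias and power.

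**Working it through.** **1. What happens to the Week 8 value.** Table 1 schedules CK at Weeks 1, 2, 4 and 8 and the clinical efficacy measures at Weeks 4 and 8. Applying SAP 5.1.1.2.3 to the End of Main Visit:

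| End of Main Visit takes place | Slot it fills | Week 8 in main analysis |
|---|---|---|
| Before the Week 4 visit | Week 1, 2 or 4 for CK; Week 4 for the efficacy measures | Missing |
| After Week 4, before the Day 57 window | Week 8 | Present, but early |
| Within the Day 57 window | Week 8 | Present and on time |

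The window is Day 57 ± 7, so it opens on Day 57 − 7 = Day 50. After a Day 29 visit, a value from Day 30 to Day 49 is labelled Week 8 although it falls outside the protocol's own window.

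**2. Reproducing the stated power.** Protocol 12.3: "A sample size of 12 subjects per group yields approximately 95% power", "using a Wilcoxon rank sum test at the two-sided 0.05 type 1 error rate". Inputs: active CK reduction normal, mean 80%, SD 8%; "4 of the placebo patients will have a percent reduction similar to the active dose group"; the other 8 placebo subjects normal, mean 10%, SD 8%. Power is the share of simulated trials with p < 0.05. With 10,000 runs the exact test gives 0.949 and the normal approximation gives 0.946 with continuity correction and 0.960 without. The 95% reproduces, but with all 24 subjects observed. Section 12.3 contains no dropout allowance.

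**3. Effect of missing Week 8 values.** The documents give no withdrawal rate, so the losses below are assumptions. Exact test, observed cases only, 5,000 runs each (simulation error about ±0.01):

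| Lost, active / placebo | Random loss | Placebo losses all non-responders |
|---|---|---|
| 0 / 0 | 0.95 | 0.95 |
| 1 / 1 | 0.90 | 0.86 |
| 2 / 1 | 0.87 | 0.82 |
| 1 / 2 | 0.84 | 0.72 |
| 2 / 2 | 0.83 | 0.68 |

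The right-hand column falls faster because the remaining placebo arm is enriched for responders: 4/12 = 33% becomes 4/10 = 40% with two non-responders lost. As in the sponsor's calculation, the test here is unstratified; the planned test is the stratified Van Elteren version.

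**4. Sensitivity trigger.** 0.15 × 24 = 3.6, so 4 subjects must lack evaluable Week 8 CK. With 3 missing (3/24 = 12.5%) the trimmed-means analysis does not run, and the 2/1 and 1/2 rows fall in that gap.

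**5. CK at the End of Main Visit.** The visit list in 7.2.2.2 names hematology, chemistry and coagulation but not CK. Table 1 includes CK at that visit. I have taken Table 1 as operative.

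**The case against.** The strongest reply is that the plan already collects an exit assessment. Anyone who permanently stops drug is called back for the full efficacy battery, and the mapping rule puts a stop after Week 4 into the Week 8 analysis. That stands. A reader might infer from 8.4.2 that every subject on the list drops out of the main analysis, each removing 1 of 12; the documents support that only for stops before the Week 4 visit. For later stops the defect is a mistimed value.

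Second, noncompliance is defined by refusal or inability to follow study procedures, not by missed doses. Some of those data would be lost under any wording, so it should not be read simply as a reason to stop drug. Inability to follow some procedures need not rule out one Week 8 visit, however, and physician decision and pregnancy are untouched by this reply.

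Third, it is tempting to say the protocol forbids these subjects to stay. The text is less settled: 8.4.2 opens by asking sites to retain subjects and get them to all scheduled visits, 8.4.1 separates declining a procedure from leaving the study, and 7.2.2.2 cites 8.4.2 for stopping drug. Drug discontinuation and study withdrawal are blurred. That is a reason to reconcile the sections, since a site following the list literally would end participation.

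Fourth, 8.4.3 permits extra enrolment and LOCF is prespecified. Extra enrolment can restore numbers but not the missing outcomes of randomized subjects, and LOCF is supplementary only.

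**Conclusion.** The conflict holds. Reasons that need not end data collection are tied to leaving the study, and no subject who stops drug is scheduled through Day 57, while the estimands ask for Week 8 regardless of discontinuation. The result is a missing Week 8 value for stops before the Week 4 visit and an early one labelled Week 8 for most later stops.

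The frequency is unknown, and a percentage of subjects affected cannot be read from the documents. The power figures rest on the sponsor's distributional assumptions, an unstratified test and assumed numbers of losses. They describe missing Week 8 CK in general, not losses attributable to the 8.4.2 list alone. Within those limits, one to three missing values can matter in a 24-subject trial without triggering the trimmed-means analysis. This should be corrected; it does not by itself invalidate the primary comparison. Nothing here bears on which events ought to stop treatment.

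**What to change.** Reconcile Protocol 8.4.2 with 7.2.2.2, Table 1 footnote 1-a and the estimands. Editing 8.4.2 alone would not be enough, because the other two provisions would still end scheduled visits.

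- Separate discontinuation of study drug from withdrawal from the study, leaving the sponsor's reasons for stopping drug unchanged.
- State that a subject who stops drug is asked to attend the remaining scheduled Main Portion visits, at least Day 57 with CK and the efficacy assessments. Exceptions: consent withdrawn, loss to follow-up, death, or participation ended at the request of the sponsor, a regulator or the IRB/IEC.
- In SAP 5.1.1.2.3, use that Day 57 value as Week 8 in place of the mapped early visit. Censoring after prohibited medication is unaffected.
- Name CK in the 7.2.2.2 visit list so that it agrees with Table 1.

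The cost is a few visits already in the schedule for subjects off drug, conforming edits to 7.2.2.2, Table 1 and SAP 5.1.1.2.3, and brief site training.

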8.4.3 REPLACEMENT OF SUBJECTS

In order to obtain an adequate number of subjects that complete the study (see Section 12.3), additional subjects may be enrolled into the study, at the discretion of the Sponsor.

9 INVESTIGATIONAL MEDICINAL PRODUCT

9.1 STUDY TREATMENT ADMINISTRATION

9.1.1 INVESTIGATIONAL MEDICINAL PRODUCT AND MATCHING PLACEBO

The IMP, zilucoplan, and the placebo will be supplied as a sterile, preservative-free, aqueous solution prefilled into 1 mL glass syringes with a 29-gauge, ½-inch, staked needle placed within a self-administration device. Subjects will be instructed to self-administer SC doses daily. Three dosage strengths of zilucoplan will be supplied as shown in [Table 4](#).

9.1.2 DOSING SCHEDULE

During the Main Portion of the study, all eligible subjects will be randomized 1:1 to receive 0.3 mg/kg zilucoplan or placebo administered SC at the Day 1 visit, which will be performed by the site staff at the study visit. Following in-clinic education and training, all subjects will self-inject daily SC doses of study drug at approximately the same time each day for the remainder of the Treatment Period.

Dosing on study visit days should be held until efficacy assessments (i.e., Physician Global Activity VAS, Patient Global Activity VAS, Proximal MMT, HAQ, 3TUG, MDAAT, and FACIT-Fatigue) and PK/PD sample collection have been completed. Patients should be supervised while injecting to ensure adequate injection technique and re-instructed if and as needed.

9.1.3 DOSE PRESENTATION

Investigational drug product will be provided in prefilled syringes for self-injection using weight bracketed dosing (i.e., subjects will be provided prefilled syringes based on their weight containing fixed amounts of zilucoplan, and each fixed amount will cover a range of subject weights). As shown in [Table 4](#), this weight bracketed dosing strategy will result in the potential for a range of doses to be received, from a minimum of 0.22 mg/kg daily (nominal dose) to a maximum dose of 0.42 mg/kg daily.

Matching placebo for the 0.3 mg/kg dose will be provided in 1 presentation of 0.574 mL.

Table 4: Zilucoplan Dose Presentations by Weight Brackets

Minimum (Nominal) Target Dose (mg/kg)	Actual Dose (mg)	Weight Range (kg)	Dose Range (mg/kg)
0.3	16.6	≥43 to <56	0.30 to 0.39
0.3	23.0	≥56 to <77	0.30 to 0.41
0.3	32.4	≥77 to 150	0.22 to 0.42

Subjects who present with a body weight outside of these ranges will be accommodated on a case-by-case basis, in consultation with the medical monitor.

9.1.3.1 MISSED DOSES

Study personnel will assess study drug compliance at every visit to record whether any doses were missed. If a subject misses 1 dose (i.e., 1 day) of study drug, he/she should take the next planned dose as scheduled and the investigator should be contacted as soon as possible. If a subject misses 2 or more consecutive doses, he/she must notify the investigator immediately and the medical monitor should be consulted.

9.2 STUDY TREATMENT MANAGEMENT

9.2.1 PREPARATION AND DISPENSING

Prefilled syringes will be dispensed to each subject at each study visit, beginning on Day 1 of the Treatment Period.

Subjects will be provided with training and detailed instructions on the administration of study drug using the single use pre-filled syringes in injection devices.

9.2.1.1 ALTERNATIVE STUDY TREATMENT SUPPLY DUE TO COVID-19 PANDEMIC

In circumstances where the subject is not allowed to visit the site, the IMP may be delivered directly to the subject via qualified courier that will act as a liaison between sites and subjects to deliver the drug during the outbreak.

If the shipment of the drug directly to the subject is agreed, the investigator or designee will clearly explain proper handling and administration of the study drug. Subjects will be instructed to return all unused IMP at the next on-site visit.

9.2.2 STUDY DRUG SUPPLY, STORAGE, AND HANDLING

Zilucoplan and placebo should be stored at 2°C to 8°C at the study site. Once dispensed to subjects, zilucoplan and placebo may be stored at room temperature [20°C to 25°C (68°F to 77°F)] for up to 45 days protected from sources of heat, light, and damage. Storage of zilucoplan and placebo outside of room temperatures should be avoided. Please refer to the study Pharmacy Manual for additional details.

Subjects will be instructed to self-inject SC doses daily at approximately the same time each day. The subject may inject study drug into the abdomen (preferred site), thigh, or upper arm.

All subjects will receive study drug kits, each of which will include 7 single-dose, prefilled syringes (pre-loaded into self-injection devices) containing study drug, alcohol wipes, and adhesive dressings, as well as a syringe disposal container.

9.2.3 DISPOSAL, RETURN, OR RETENTION OF UNUSED DRUG

Subjects will receive secure containers to dispose of used syringes while at home. At each visit, the subject should return the container containing all used syringes to the site. The unused study drug (i.e., unused syringes) should be retained by the subject.

All unused study drug syringes and disposal containers containing used syringes must be returned to the site at the last study visit for each Treatment Period (i.e., Day 57/End of Main Visit or the Final Extension Visit).

9.2.4 DRUG ACCOUNTABILITY

It is the responsibility of the pharmacist to ensure that a current record of inventory/drug accountability is maintained. Inventory records must be readily available for inspection by the study monitor and are open to inspection by regulatory authorities at any time. For further details, please consult the Pharmacy Manual.

10 STUDY ASSESSMENTS

Please refer to [Table 1](#) and [Table 2](#) for the timing of study assessments.

10.1 SUBJECT AND BASELINE DISEASE CHARACTERISTICS

10.1.1 MEDICAL HISTORY AND DEMOGRAPHICS

Relevant medical history (including surgical history) will be documented at the Screening visit to assess subject eligibility. The following demographic data will be collected: year of birth, gender, ethnicity, and race.

The screening assessment will also include disease history with documentation of the diagnosis of IMNM, disease course and any IMNM-specific treatments. Muscle biopsy findings (including presence or absence of C5b-9 staining) and other diagnostic tests (e.g., MRI, serology, and electromyography) will also be recorded.

10.1.2 HEIGHT AND WEIGHT

Height (cm) will be collected at the Screening visit only. Weight (kg) will be measured at the study visits indicated in [Table 1](#) and [Table 2](#).

10.1.3 PRIOR AND CONCOMITANT MEDICATIONS

Subjects are prohibited from receiving another complement inhibitor, rituximab, statins, or any investigational medicinal product while on study. All other medications are permitted while on study.

Subjects are expected to remain on stable doses of permitted SOC therapy for IMNM throughout the Main Portion of the study and through the Week 8 visit of the Extension Portion, including corticosteroids, immunosuppressive drugs, and IVIG. The medical monitor should be contacted prior to any changes throughout the duration of the study in IMNM specific therapy.

All prescriptions and over-the-counter medications taken during the 30 days prior to Baseline (i.e., Day 1) through the last study visit will be documented. NOTE: A complete history of medications taken for the treatment of IMNM will be collected.

Concomitant medications include any prescription or over-the-counter medication that is ongoing on Day 1 or that is initiated following the first dose of study drug on Day 1.

Medications, including over-the-counter therapeutics, natural products, and vitamins, should not be changed during the Screening or Treatment Periods, unless medically

necessary. All concomitant medications necessary for the health and well-being of a subject will be permitted.

Medications will be recorded on the subject's source documents and entered on the appropriate eCRF. Any changes to concomitant medications will be recorded in the eCRF. Physical therapy interventions and medical devices are considered concomitant interventions and will be captured in the concomitant medications eCRF.

